#### **PROTOCOL AMENDMENTS HISTORY**

After the protocol has been approved by the Research Ethics Committee no substantial amendments may be made without the documented agreement of the investigators, the Sponsor and the Research Ethics Committee.

Date	Version	Rationale	Author

## 1 BACKGROUND AND RATIONALE

Historically, mpox [1] (previously known as monkeypox or MPX) has occurred in children and adolescents (as well as adults) living in endemic regions. Although the clinical presentation is expected to be similar in children as in adults, it is not known whether children are at greater risk of infection, disease, or severe outcomes. Rare complications of mpox include encephalitis, cellulitis, pneumonia, sepsis, abscess, airway obstruction due to severe lymphadenopathy, keratitis, and corneal scarring [2].

Vertical transmission of mpox virus has been documented [3, 4], but the natural history of congenital mpox is unknown. It is also noted that immunocompromising conditions and certain skin conditions, such as eczema, are associated with increased severity of mpox disease in adults and children, although there are limited data on risk factors for infection specifically amongst children and adolescents.

To date, the only antiviral drug licensed for treatment of mpox is tecovirimat. This is available in some countries for treatment of mpox in adults and children weighing more than 13 kg, but data on effectiveness in humans (and particularly children) are limited. There are currently no data on post-exposure and pre-exposure prophylaxis (PEP/PrEP) to prevent mpox in children, and there are no vaccines or other products currently licensed for mpox prevention in children or adolescents. The state of knowledge regarding this infection and its associated disease in these groups is limited and, considering the 2022 global outbreak and potential for ongoing transmission, it is crucial to rapidly collect harmonised data to better define the disease course and characteristics and identify any changes in epidemiology and variations between settings.

To date, no harmonized European or global paediatric clinical protocol for data collection and follow-up of children and adolescents diagnosed with mpox has been established and there are currently very limited data on the efficacy and safety of interventions for the treatment and prevention of mpox, including vaccines, for children and adolescents. The lack of a common protocol hampers the response to the outbreak, for two reasons. Firstly, to date, numbers of children and adolescents diagnosed with mpox have been small. Second, outputs from different studies and systems may be difficult to compare due to differences in factors such as study design, data collected, and variable definitions; synthesising this disparate evidence to inform policies regarding treatment and mitigation measures is then extremely challenging.

The primary objective of this study is to use a harmonised data collection system to describe the presentation, clinical course and outcomes of laboratory-confirmed mpox virus infection in infants, children and adolescents. Such a protocol can be used for purposes of surveillance and assessment of clinical symptoms, severity of disease and effects of treatment. In the future, if vaccines become more widely used in children and adolescents, it will also allow preliminary assessment of vaccine effectiveness. Finally, the data collected can also serve as a sampling frame from which to recruit participants into additional studies, for example of vaccine immunogenicity and safety, and trials.

The involvement of sites from different settings will enable capture of any epidemiological differences associated with factors such as geographic location, country income, and mpox endemic status. Physicians from participating sites will also be encouraged to report to relevant authorities any adverse events potentially related to any intervention used in routine care, where possible including an assessment of causality. This will be helpful in better defining the safety profiles of these interventions.

The longer-term intention is that this protocol and database will be adapted and used for other emerging or re-emerging infections in children, where case numbers may initially be low, warranting a centralised repository approach.

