##### **Phase 2 observational study.**

When Phase 2 is activated, it will be implemented at each participating site when all required approvals are in place. Phase 2 consists of the development of a prospective observational study which will collect the same data as for the Phase 1 registry, as well as additional data such as dates of events and date of birth which are considered pseudonymised data. For this reason, informed consent/assent will be required from participants and/or their legal guardian. Patients (and/or their legal guardian) may be asked for permission to link their data to other medical records, and to be contacted for further research studies.

If the patient/legal representative does not give consent to participate in Phase 2, the study team will proceed with entering data only into the Phase 1 anonymous registry database.

The eCRF will be based on routine patient visits, and all visits from initial presentation (diagnosis or admission) onwards (follow-up visits) will be entered, until the infant, child or adolescent is considered fully discharged from care (outcome visit). Follow-up of infants born to adolescent mothers who acquired mpox in pregnancy to ascertain neonatal outcomes should end at or before day 28 after the baby is born. If consent is sought for collecting detailed information on infants who acquired mpox and whose mothers are already recruited in the study, linkage of maternal study ID and infant study ID will be made (see section 6.1 for more details).

Only routinely collected clinical data will be entered in the database.

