## 4 ELIGIBILITY CRITERIA

All patients with laboratory-confirmed mpox infection seen in hospitals as well as primary/community care settings will be eligible for inclusion in Phases 1 and 2.

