### 4.1 INCLUSION CRITERIA

For the Phase 1 registry all infants, children and adolescents aged <18 years at the time of mpox diagnosis, with laboratory-confirmed mpox infection, as per national guidelines, will be eligible for inclusion in the anonymised dataset. Moreover, mothers of eligible infants who are diagnosed with mpox at 28days or less are included in the study to collect maternal data on pregnancy and delivery..

For the Phase 2 observational study all patients meeting the inclusion criteria for Phase 1 will be eligible for inclusion. Patients and their legal guardians will be required to give informed consent/ assent.

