### **7.2 SAMPLE SIZE**

In Phase 1, the preliminary analysis will be largely descriptive. Therefore, no formal sample size calculation has been undertaken, and instead all available data on cases will be utilised. Future specific analyses in Phases 1 and 2 will be assessed for feasibility based on the numbers of cases reported and their characteristics (e.g. numbers with and without a particular exposure of interest, such as age or vaccination).

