### **7.3 ANALYSIS PLAN**

Analysis of the data collected in Phases 1 and 2 will be primarily descriptive, including summaries of:

- Age, sex/ gender, temporal and geographical distribution of children and adolescents with laboratory-confirmed mpox infection
- Description of clinical symptoms, including number of lesions
- Frequency of specified outcomes, including proportion hospitalised and admitted to ICU
- Likely mode of mpox acquisition
- Treatments administered, including use of tecovirimat, its duration and outcomes following treatment
- Number of infants with congenital infections, and description of maternal and infant characteristics

If numbers allow, additional analyses will assess the association between patient characteristics / interventions and outcomes, for example comparing the odds of severe outcomes between patients who did and did not receive specific antiviral treatments or who were versus were not vaccinated, using multivariable logistic regression.

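### Does a registry of confirmed cases contradict itself by saying it will allow preliminary assessment of vaccine effectiveness?

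*Protocol*

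**What the plan says.** Section 1 (Background and rationale) lists uses of the protocol: surveillance and the assessment of symptoms, severity and treatment effects. It then adds: "In the future, if vaccines become more widely used in children and adolescents, it will also allow preliminary assessment of vaccine effectiveness". It does not say whether this means effectiveness against infection, disease or severe outcomes.

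Eligibility is set in section 4: "All patients with laboratory-confirmed mpox infection seen in hospitals as well as primary/community care settings will be eligible". Section 4.1 limits Phase 1 to those under 18 years "with laboratory-confirmed mpox infection, as per national guidelines, will be eligible for inclusion in the anonymised dataset", and continues: "For the Phase 2 observational study all patients meeting the inclusion criteria for Phase 1 will be eligible for inclusion". Two further groups appear. Mothers of infants diagnosed at 28 days or less contribute pregnancy and delivery data (section 4.1), and offspring of adolescents infected in pregnancy are followed for neonatal outcomes (section 3.1). Neither is a comparison group for vaccination.

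Section 7.2 makes later specific analyses depend on feasibility, judged by "numbers with and without a particular exposure of interest, such as age or vaccination". Section 7.3 gives the only vaccine analysis, to be done if numbers allow, by multivariable logistic regression: "comparing the odds of severe outcomes between patients who did and did not receive specific antiviral treatments or who were versus were not vaccinated".

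Vaccine effectiveness does not appear in the objectives (sections 2.1.1 and 2.1.2) or the outcome measures (section 7.1).

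**The concern.** Vaccine effectiveness is usually understood as prevention of infection or disease. Estimating it requires vaccination status in people without the disease, whether from controls, a cohort denominator or population coverage. The protocol describes none of these. Record linkage in Phase 2 is to the medical records of consenting patients, and Phase 3 sub-studies are nested in Phase 2, so neither supplies uninfected children as written.

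The worry is that a later analyst links the sentence in section 1 to the odds ratio in section 7.3 and reports one minus that odds ratio as effectiveness. A vaccine that prevented most infections but did not alter the course of breakthrough cases would then look useless, in a population for which the protocol says there is little vaccine evidence. The protocol is also meant to be adapted for other infections, so loose wording could carry over.

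**Working it through.** The protocol gives no vaccine effect, coverage or severity figure, so there is nothing to reproduce. The question is what case-only data can identify. All numbers below are assumptions for illustration.

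**1. Does the section 7.3 odds ratio contain effectiveness against infection?** Let unvaccinated cases number n0 and vaccinated cases, per equal number exposed, n1 = n0(1 − VE). Let the severe risk be p0 in unvaccinated cases and RR × p0 in vaccinated cases. Then

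OR = [RR·p0 / (1 − RR·p0)] / [p0 / (1 − p0)].

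Both n0 and n1 drop out, and VE with them.

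- RR = 1: OR = 1.0 for any p0 and any VE.
- RR = 0.5, p0 = 5%: (0.025/0.975)/(0.05/0.95) = 0.487.
- RR = 0.5, p0 = 10%: (0.05/0.95)/(0.10/0.90) = 0.474.
- RR = 0.5, p0 = 20%: (0.10/0.90)/(0.20/0.80) = 0.444.

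**2. The same in counts.** Take 100,000 children, 30% vaccinated, an attack rate of 0.2% in the unvaccinated, and 20% of cases severe in both groups. Unvaccinated cases: 70,000 × 0.002 = 140. Vaccinated cases: 30,000 × 0.002 × (1 − VE).

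| True VE against infection | Vaccinated cases | OR for severity among cases | Population VE against severe disease |
|---|---|---|---|
| 0% | 60 | 1.0 | 0% |
| 50% | 30 | 1.0 | 50% |
| 80% | 12 | 1.0 | 80% |

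**3. What would mislabelling cost?** With VE = 80% and RR = 0.5, true effectiveness against severe disease is 1 − 0.2 × 0.5 = 90%. One minus the case-only OR gives 1 − 0.487 = 51% to 1 − 0.444 = 56%.

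**4. Can registry data contribute to effectiveness at all?** Yes, through the screening method, which sets the odds of vaccination among cases against the odds in the population: VE = 1 − [PCV/(1 − PCV)] / [c/(1 − c)]. Here PCV is the vaccinated share of cases and c is coverage.

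- With true VE 80% and true coverage 20%, PCV = 0.04/(0.04 + 0.80) = 4.76%, odds 0.05. Then VE = 1 − 0.05/0.25 = 80%.
- If coverage is wrongly taken as 10%: 1 − 0.05/0.1111 = 55%. If taken as 30%: 1 − 0.05/0.4286 = 88%.
- With PCV = 10% and coverage unknown, the estimate runs from 1 − 0.1111/0.0526 = −111% at 5% coverage to 1 − 0.1111/1 = 89% at 50% coverage.

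The registry can supply the case side, since sections 7.2 and 7.3 foresee age, time, place and vaccination status. Coverage must come from outside.

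**5. Does the plan mislabel anything?** Section 7.3 names the endpoint (severe outcomes), the population (patients in the study), the measure (odds), the model, and the aim (association). Nowhere does the protocol turn that odds ratio into an effectiveness figure, so the gap in step 3 arises only if someone departs from the text.

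**The case for a change.** The strongest case for a change is that the innocent reading of section 1 is strained. Severity and treatment effects have already been listed when the vaccine sentence adds effectiveness as a further use, and the surrounding text treats vaccines as preventive. Many readers will therefore think of prevention. Eligibility is fixed in the protocol, so an analysis plan could bring in external coverage but could not add uninfected participants. Rewording would cost a sentence or two.

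Much of this stands. The term is unqualified, and the registry's data by themselves support only a comparison of severity among cases.

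It does not make the sentence false. The remark is set in the future, depends on wider vaccine use, and claims only that a preliminary assessment will be possible. A case registry that records vaccination status does make a screening estimate possible once coverage figures exist. Choosing the coverage source, and deciding which doses count as given before exposure, belong to that later analysis. Section 7.2 leaves such analyses to feasibility, section 9 provides a proposal route for new ones, and section 2.1.3 gives each sub-study its own protocol. Dose timing is a separate matter of defining exposure. Phase 2 will hold "additional data such as dates of events and date of birth which are considered pseudonymised data", and what the Phase 1 form records cannot be judged from the protocol.

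**Conclusion.** No change is needed. The identifiability point is correct and does not depend on the illustrative inputs: effectiveness against infection cancels from any case-only severity odds ratio. The potential misreading is large under the assumed figures (51% to 56% against a true 90%), but it requires an analyst to relabel a result that section 7.3 describes properly. Followed as written, the plan yields a conditional comparison of severity by vaccination status among cases, offered as an association and only if numbers allow.

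No objective, outcome measure or planned analysis is wrong. Saying in section 1 which effect is meant would be a courtesy to readers and would change no result. This conclusion assumes that any later effectiveness analysis is specified with its own coverage data or comparison group, as any competent analyst would require before reporting such a figure.

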## 2 AIM AND OBJECTIVES

The overall aim of this study is to increase knowledge about mpox infection and its associated disease in infants, children and adolescents. This will be done through the development of a harmonized system that will allow collection of information on demographics, clinical symptoms, clinical course, treatments and outcomes.

The study will be carried out in three potential phases:

- **Phase 1:** rapid development of an online paediatric registry for collection of data on mpox in infants, children and adolescents. This will allow harmonised collection of anonymised routine clinical data on infants, children and adolescents with laboratory-confirmed mpox infection, including adolescent girls who acquired mpox in pregnancy, and infants who acquired mpox through vertical transmission. Data to be collected include clinical characteristics, disease severity, treatments received and outcomes. All data will be fully anonymised, allowing rapid implementation in many countries without the need for ethics approval, where applicable.
- **Phase 2:** if more detailed prospective data collection would aid the public health response, an enhanced observational study of infants, children and adolescents with confirmed mpox infection (as in Phase 1) will be established. This will be a consented study collecting detailed pseudonymised data over the course of the infection. The decision about whether to carry out phase 2 will be based on the ongoing case numbers and the existence of other surveillance systems/studies.
- **Phase 3:** initiation of nested sub-studies within the consented observational study (Phase 2) to investigate specific research questions in this population, including collection of samples, where necessary, for analysis and/or storage in a biobank. Each sub-study will require its own protocol and informed consent.

The database, networks and systems developed within Phases 1 to 3 will be flexible and designed to be readily adapted to data collection for other emerging and re-emerging infections in children.

### 2.1 PRIMARY OBJECTIVES

#### 2.1.1 Phase 1 registry

- To describe anonymised data on paediatric and adolescent patients with mpox infection to inform approaches to infection control and prevention during this and future outbreaks, depending on case trajectories, with flexibility to adapt to other (re-) emerging infections in the future. Depending on the numbers reported, this may include:
  - a. monitoring the temporal and geographical distribution of mpox infection in the paediatric and adolescent population, including in specific paediatric/adolescent groups, such as those with underlying conditions or with vertically acquired mpox;
  - b. describing the epidemiology and clinical presentation of the infection/ disease, including outcomes of treatment administered as part of routine care;
  - c. describing the populations at highest risk of severe outcomes, including identifying factors associated with severe disease and death;
  - d. describing characteristics and outcomes of infants with vertically acquired mpox infection.

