### **2.1.2 Phase 2 observational study**

- To describe pseudonymised data on paediatric and adolescent patients with mpox infection in terms of presentation, clinical course, and outcomes. Depending on the numbers reported, this may include:
  - a) monitoring the temporal and geographical spread of cases of mpox infection in the paediatric and adolescent population, including in specific paediatric groups, such as those with underlying conditions;
  - b) describing the epidemiology and clinical presentation of the infection, including outcomes of treatment administered as part of routine care;
  - c) describing the populations at highest risk of severe outcomes, including identifying factors associated with severe disease and death;
  - d) among mpox patients who are pregnant, describing the infection status of offspring (and estimating vertical transmission risk, if feasible), and characteristics and outcomes of infants with vertically acquired mpox infection.

The Phase 2 consented study will allow collection of pseudonymised data allowing more detailed analyses than are possible in Phase 1 (unconsented and anonymised).

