##### **Phase 1 registry.**

An online registry will be developed to collect anonymised routine clinical data on patients with laboratory confirmed mpox infection aged <18 years. This may include pregnancy and neonatal data both for adolescents who are pregnant or up to 28 days postnatal and have mpox, and infants diagnosed with mpox in the neonatal period. Because all data collected will be fully anonymised, ethics approval may not be required in some or all countries, allowing swift implementation of the registry in response to an outbreak.

Data to be collected include clinical characteristics, symptoms and disease severity, treatments received and outcomes. Data for each patient will be reported at a single point in time, at the end of the clinical episode (e.g. at discharge from care). Data will be collected on historic cases (occurring before the inception of the registry), and on incident cases where relevant approvals and/or consent have not been obtained for Phase 2. Only routinely collected clinical data will be reported.

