## 6 DATA MANAGEMENT

### 6.1 REDCAP

Source documents are represented by documents where data are first recorded, and from which participants' electronic case report forms (eCRF) data are obtained. These include, but are not limited to, hospital records (from which medical history and previous and concurrent medication may be summarised into the CRF).

In this study, primary data sources are collected in eCRFs completed by study staff at participating sites. Source data will be collected directly into a web-based REDCap database specifically designed by the study team. A separate but interoperable REDCap database will be developed for each phase: 1) the unconsented, anonymised data, 2) consented, pseudonymised data, and 3) each additional sub study initiated in Phase 3 (each to be described in its own protocol).

To enhance accuracy, data will be subjected to logic and consistency checks, e.g., for implausible values and inconsistencies. Potential errors will be investigated and discussed between the data manager, statisticians, and individual sites.

In Phase 1, data for each patient will be entered at the end of clinical follow-up and each clinical site will transcribe into the eCRF only anonymous retrospective data from source data. No personal identifiable data will be entered into the eCRF (e.g., date of birth will be replaced with age group at diagnosis).

[figure not shown]
In Phase 2, pseudonymised data will be collected. The 'Initial Presentation Form' in REDCap should be completed as soon as possible and thereafter, each site can decide to perform the data entry following each patient visit or as in Phase 1, at the point of patient discharge from care.

In Phase 1 data will be fully anonymous therefore no identifiers will be recorded, whereas in Phase 2 the participants will be identified by a unique study-specific number and/or code in any database. The name and any other identifying detail will be retained only by the site staff on the consent form and the clinical records.

Phase 2 maternal-infant record linkage: If consent is sought for collecting detailed information on an infant with mpox whose adolescent mother has mpox and is already recruited in the study, the mother's study ID should be reported by the study staff on the newly generated infant record, to allow for linkage of maternal study ID and infant study ID.

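### Can the Phase 1 registry describe cases over time if dates of events are collected only in Phase 2?

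*Protocol*

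**What the plan says.** The temporal aim is set separately for each phase. For Phase 1, Section 2.1.1(a) names "monitoring the temporal and geographical distribution of mpox infection in the paediatric and adolescent population", as one of several items that may be included if numbers allow. For Phase 2, Section 2.1.2(a) has "monitoring the temporal and geographical spread of cases of mpox infection in the paediatric and adolescent population", under the same condition. Section 7.3 then opens with "Analysis of the data collected in Phases 1 and 2 will be primarily descriptive, including summaries of" and lists, without that condition, the "temporal and geographical distribution of children and adolescents with laboratory-confirmed mpox infection".

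On data items, Section 3.1 says that Phase 2 collects what Phase 1 collects and also "additional data such as dates of events and date of birth which are considered pseudonymised data". Section 6.1 gives the Phase 1 rule: "No personal identifiable data will be entered into the eCRF (e.g., date of birth will be replaced with age group at diagnosis".

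On timing, Section 3.1 says of Phase 1: "Data for each patient will be reported at a single point in time, at the end of the clinical episode". It also says: "Data will be collected on historic cases (occurring before the inception of the registry", so part of the registry is filled in retrospectively.

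**The concern.** Section 3.1 names two items that Phase 2 adds and classes both as pseudonymised: dates of events and date of birth. For date of birth, Section 6.1 names the Phase 1 replacement, an age group. For dates of events, no section names one. Yet the temporal summary is planned for Phase 1 data as well.

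If Phase 1 really held no calendar item, the loss could matter. Phase 2 is conditional (Sections 2 and 3.2), so Phase 1 may be the only source. Even if Phase 2 opens, historic cases and patients without Phase 2 approval or consent are recorded only in Phase 1. The background section wants the data to reveal changes in epidemiology, which requires knowing when cases occurred. The only calendar time that the text implies for a Phase 1 record is the time of entry, since Section 6.3 makes entries auditable, and that is not the time of the case.

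**Working it through.** The protocol gives no sample size, power or other figure on this point, so there is no number to reproduce. The check is a comparison of the sections, followed by a small calculation for scale.

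**1. Does the data rule conflict with the temporal aim?** The rule in Section 3.1 concerns dates of events. The aim in Sections 2.1.1(a) and 7.3 is a distribution over time, with no granularity fixed. A distribution by month, quarter or year needs only the period of diagnosis. Section 3.2 plans about 18 months of data collection, which gives

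- by month: 18 / 1 = 18 intervals;
- by quarter: 18 / 3 = 6 intervals;
- by year: 18 / 12 = 1.5 intervals.

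Historic cases add earlier intervals. Months or quarters would therefore show a trend without exact dates. No sentence in Sections 2, 3.1, 5 or 6.1 excludes such an item. The rule and the aim can both be met as written.

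**2. Is the single named replacement a complete list?** No. The Phase 1 rule in Section 6.1 is general, and the age group is introduced as an example. The Phase 2 additions in Section 3.1 are also introduced as examples. Counting one replacement for two additions compares two open lists and shows nothing about what the form holds.

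**3. Does silence in the Phase 1 data lists mean that an item is not collected?** Sections 2 and 3.1 list categories: clinical characteristics, symptoms, severity, treatments, outcomes. Set against Section 7.3:

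| Needed for Section 7.3 | Named in the Phase 1 lists of Sections 2 and 3.1? |
|---|---|
| Period of diagnosis | No |
| Country or region | No (country might be known from the site account) |
| Likely mode of acquisition | No |
| Vaccination status (if numbers allow) | No |
| Duration of tecovirimat treatment | No, only treatments in general |

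If silence meant absence, most of these summaries would fail too. The lists are not a dictionary of variables. The last row also shows that a quantity based on time can be held without dates, for instance as a number of days.

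**4. How bad would entry time be?** Historic cases occurred before the registry began and are entered after it, so entry time would put all of them on the wrong side of the opening, by definition. For incident cases, with diagnosis spread evenly within a period of length P and a constant lag d shorter than P, the share moved to the next period is d / P. The protocol gives no lag; d = 7 to 28 days is an assumption.

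- Month: 7 / 30.44 = 23% to 28 / 30.44 = 92%.
- Quarter: 7 / 91.31 = 8% to 28 / 91.31 = 31%.
- Year: 7 / 365.25 = 2% to 28 / 365.25 = 8%.

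These figures show why entry time should not serve as the time axis. They do not describe the plan: no section proposes it, and the sentence on auditable entries stands in a section about data security.

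**The case for a change.** The best argument for a change is that this concerns what is collected, not how it is analysed. An analysis plan cannot restore a period that was never recorded. Recovery would also be hard: Phase 1 holds no identifiers (Section 6.1), and Section 5 says that patients already in Phase 1 will not be approached for Phase 2. The protocol itself draws the line between anonymised and pseudonymised data, puts dates on the Phase 2 side, and names a substitute for the neighbouring item only. Section 7.3 plans the temporal summary without the condition on numbers, so the optional wording in Section 2.1.1 does not remove the question. Section 1 also names differences in data collected and in variable definitions as the problem that a common protocol should solve.

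Much of this stands as description: dates are assigned to Phase 2, no coarser period is named, and a period left off the form would be difficult to recover. The step to a defect does not stand. It needs the further premise that the form lacks the item, and nothing in the protocol says so. The form is a separate study document and is not at hand. Restricting the temporal aim to Phase 2 would cost more than it gains, since it would drop the historic cases and tie a surveillance aim to a phase that may never start.

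**Conclusion.** The concern does not call for a change. The protocol leaves one Phase 1 field unnamed; it does not contradict itself. A month, quarter or year of diagnosis is compatible with every stated rule, serves the temporal aim, and is the obvious choice for a registry that plans to describe cases over time and to accept historic ones. The choice of width, with a check that period, country and age group together remain anonymous, is ordinary work for the case report form.

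The size of the issue is a point of clarity. No estimate, test or stated figure changes. The percentages for entry time apply only if the form has no period and analysts use the entry stamp instead, neither of which the protocol says. The conclusion assumes that the form, which is not shown, holds such a period or will do so. If it were found to hold none, the matter would be a real gap in the form and would deserve prompt attention there. Naming the period in Section 6.1 would help a reader, but the plan does not depend on it.
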